3.2.2 Post-period

During the post-period, all enrolled subjects will receive treatment for ABSSSI with dalbavancin at each participating site. Dalbavancin will be administered as a single IV dose of 1500 mg over 30 minutes (1125 mg over 30 minutes if CrCl <30 mL/min, for those not on regularly scheduled dialysis).¹² Dalbavancin will be provided to sites by study sponsor.

3.2.3 Rationale of dose/regimen of antibiotic treatment

Usual care antibiotic therapy and dalbavancin will each be administered per relevant guidelines/manufacturer instructions (dosing provided in Table 1). Duration of treatment with usual care will be left to the physician's discretion, as recommendations for several agents include a range (e.g., 10–14 days for linezolid).²⁴

3.2.4 Rationale for choice of comparator

Usual care will comprise investigator's choice of care and may therefore vary from subject to subject. This was selected to allow for comparisons of the new critical pathway, which includes use of dalbavancin, with "real world" treatment.

3.3 Subject identification

Patients admitted to the hospital with an ABSSSI infection during both the pre- and post-periods will be assessed for inclusion and exclusion criteria. These criteria will be prepared as an annotated checklist for the study coordinator and/or study nurses to implement and document using a CRF. Information obtained through the annotated checklist coupled with physician assessment will define guideline-based patient identification criteria.

3.3.1 Pre-period

During the pre-period, the study coordinator and/or other study nurses will identify patients who may be eligible for the study. All hospital staff may be reminded (through posters or memorandums) to inform the study coordinator and/or other study nurses as soon as an ABSSSI patient is admitted. The study coordinator will implement inclusion and exclusion criteria for the new critical pathway by patient interview and/or chart review. Inclusion criteria includes clinical judgment that patient requires coverage for a known or suspected Gram-positive infection. Patients who meet all inclusion criteria and none of the exclusion criteria based on study coordinator assessment will be enrolled in the study or flagged for further review by core study team physicians, who will make the final enrollment decision. The treating physician will be blinded to protocol content and study enrollment decision. Study coordinator will then complete all additional elements of enrollment, including informed consent, and scheduling of follow-up.

3.3.2 Post-period

During the post-period, the study coordinator and/or other study nurses will identify patients who may be eligible for the study. As in the pre-period, physicians or other appropriate healthcare providers may also identify subjects who are eligible for the study. All hospital staff may be reminded (through posters or memorandums) to inform the study coordinator and/or other study nurses as soon as an ABSSSI subject is admitted to the hospital. The study coordinator or treating physician will implement the checklist and enroll subjects into the study. Study coordinator will then complete enrollment, including informed consent, and scheduling of follow-up.

3.3.3 Subject follow-up

Within both the pre- and post-periods, follow-up for each subject will begin on the day of enrollment (which is anticipated to be the date of treatment initiation) and conclude 44 days thereafter. Follow-up will therefore include the presumed “episode” of antibiotic therapy for ABSSSI (up to 10-14 days) and subsequent 30-day period.

3.3.4 Rationale for subject follow-up

Each subject will be followed for a 10-14-day period (i.e. initial care), which is the longest supported duration of antibiotic therapy for ABSSSI treatment.¹⁵ In order to allow similar opportunity for collection of outcomes in the pre- and the post-period, the post-period similarly assumes 10-14 days. The addition of 30 days after initial care (i.e. follow-up) was thought to comprehensively assess outcomes during a relevant timeframe after the completion of antibiotic therapy. Therefore, 44 days (initial care and follow-up) for each

subject encompasses both the maximum treatment duration and assessment of relevant outcomes in the 30 days following treatment.

3.4 Subject inclusion and exclusion criteria

Study subjects will be recruited among admitted patients with ABSSSI and who require coverage for a known or suspected Gram-positive infection. Among all such individuals, attention will be focused on those who meet all of the inclusion criteria and none of the exclusion criteria.

3.4.1 Inclusion criteria

Eligible study subjects satisfy all of the following inclusion criteria^{1,10,24}

- Aged ≥ 18 years
- Admitted patients who meet clinical definition for ABSSSI¹⁰⁻¹¹
 - Present with the following infection types: cellulitis/erysipelas, wound infection, or major cutaneous abscess
- Known or suspected infection caused by susceptible isolates of the following Gram-positive microorganisms: *Staphylococcus aureus* (including methicillin-susceptible and methicillin-resistant strains), *Streptococcus pyogenes*, *Streptococcus agalactiae*, *Streptococcus dysgalactiae*, *Streptococcus anginosus group* (including *S. anginosus*, *S. intermedius*, *S. constellatus*) and *Enterococcus faecalis* (vancomycin susceptible strains).
- Willing and able to return to the hospital or a designated clinic for scheduled visits, or be in contact with the study coordinator through telephone communication, as required by the protocol and the antibiotic treatment administered

3.4.2 Exclusion criteria

Study subjects with any of the following criteria will be excluded^{1,12-14}

- [REDACTED]
- Known or suspected Gram-negative infections including bacteremia, anaerobic infections, or fungemia, even in the presence of Gram-positive infection
- Known or suspected infections that are severe, life-threatening, or are not included in the ABSSSI FDA guidance, including the following examples:
 - [REDACTED]
 - [REDACTED]
 - [REDACTED]
 - [REDACTED]
 - [REDACTED]

• [REDACTED]

■ [REDACTED]

• Injection drug users presenting with a fever

■ [REDACTED]

^a If the patient is a woman of child-bearing potential, from at least the first dose of study drug until the final visit she must confirm strict abstinence from sexual intercourse with any male or must confirm use of an effective contraceptive method from the following list: A barrier (condoms, diaphragm or cervical cap) with spermicide; Oral or similar contraceptive, which includes, but is not limited to: injectable, implanted, or patch hormone therapy, and intrauterine device (IUD); Documented surgical sterilization at least 4 weeks prior to baseline; Partner vasectomy at least 6 months prior to baseline.

- Severe neurological disorder leading to severe immobility or confined to wheelchair or bed (e.g. paraplegia and hemiplegia)
- Bilateral lower extremity involvement of the suspected infection (to exclude patients with chronic venous stasis)
- Unwilling or unable to follow study procedures

4.1 Study outcomes

4.1.1 Baseline characteristics

Baseline characteristics will be collected following subject enrollment into the study, and will be based on physical examination and medical history. A complete list of baseline characteristics is shown in Table 2.

Table 2. Baseline characteristics

Measure Type	Description
Demographics	Age (in years) Gender Race Employment status Location subject presents from (e.g. from home, LTC, SNF, nursing home)
Comorbidities	Myocardial infarction Congestive heart failure Peripheral vascular disease Cerebrovascular disease Dementia Chronic pulmonary disease Rheumatologic disease Peptic ulcer disease Mild liver disease Diabetes without complications Diabetes with complications Renal disease Moderate or severe liver disease (Child-Pugh Class B and C) Any malignancy, including leukemia and lymphoma Metastatic solid tumor If subject has cancer, whether active vs. remitted/cured Alcohol/drug abuse/illicit needle use Malnutrition HIV

Measure Type	Description
	Immunocompromising conditions other than HIV Altered mental status
Charlson Comorbidity Index ^b (CCI)	Derived variable based on recorded comorbidities: Calculation of the CCI for each subject at baseline to assess the risk of 1 year mortality
Infection type	Cellulitis/erysipelas, wound infection, or major cutaneous abscess
Infection characteristics	Lesion size (as described in Appendix A) and location Thrombocytopenia (<150,000 platelet count or site-specific definition) Hyperglycemia (>120mg/dL blood glucose or site-specific definition) Hyponatremia (<135 mEq/L blood sodium or site-specific definition) Acidosis (<7.35 pH of the blood or site-specific definition or described in medical chart) Uremia (as described in medical chart) Anemia (14-18 g/dL hemoglobin for men or 12-16 g/dL hemoglobin for women or site-specific definition) Fever (>98.6 degrees Fahrenheit or site-specific definition) SIRS criteria ^c at enrollment, including highest or lowest recorded RR and highest or lowest recorded BPM/highest or lowest recorded fever/highest or lowest WBC count or amount of immature cells Highest or lowest recorded BP at enrollment Laboratory results at baseline and during follow-up (e.g. Total white blood cell count, hemoglobin, sodium, glucose, serum creatinine, and C-reactive protein)

^b Deyo et al 1992

^c SIRS criteria include abnormalities in temperature, heart rate, respiration, and white blood cell count. Specifically, fever >38.0°C or hypothermia <36.0°C, tachycardia >90 beats/minute, tachypnea >20 breaths/minute or PaCO₂ of less than 32mmHg, abnormal white blood cell count leukocytosis >12,000/microliter, leucopenia <4,000/microliter, or >10% immature cells (bands).^{26,27}

Measure Type	Description
	
Rapid microbial assay and microbiological culture results and type of culture (i.e. blood, wound swab, urine) at baseline and during follow-up
 
Presence of recurrent infection (evidence from chart review, provider assessment and subject report of a similar ABSSSI in the same location on the body) and any ABSSSI infections in the prior 6 months

Healthcare utilization in prior three months	
Hospitalizations and primary reason
 
Surgical interventions and primary reason
 
Admission to the ICU and primary reason
 
ED visits or other outpatient visits (e.g., infusion center and physician’s office) and primary reason
 
Use of dialysis
 
Use of any medications for chronic diseases and specifically use of an antibiotic medication
 
Prior antibiotic treatment failure
 
Receipt of wound care for the presenting infection

[figure not shown]
4.1.2 Primary and secondary outcomes

Primary and secondary outcomes are presented in in Table 3. Outcomes will be assessed during initial care (the date of enrollment to 10-14 days) and follow-up (30 days after initial care) unless otherwise specified.

Table 3. Primary and secondary outcomes

Measure	Description
Infection-related total admitted hospital days during initial care and follow up	Includes days during the initial hospitalization and all other hospitalizations
Total admitted hospital days during initial care and follow up	Includes days during the initial hospitalization and all other infection-related hospitalizations
	Number of major unexpected surgeries
	Number of major expected surgeries

Measure	Description
Infection-related major surgical interventions that required operating room time during initial care and follow up	Number of all major surgical interventions unexpected or expected
Infection-related hospitalizations during initial care and follow up	Number of infection-related hospitalizations
Infection-related hospitalizations during initial care and follow-up that resulted in admission to Intensive Care Unit (ICU)	Number of infection-related hospitalizations resulting in admission to the ICU.
All cause hospitalizations in the 30 days post discharge from the hospital	Number of all hospitalizations for subjects including re-hospitalizations
Infection-related ED visits during initial care and follow up	Number of unexpected visits to ED
	Number of expected visits to ED
	All visits (unexpected and expected) to ED
Infection-related outpatient healthcare visits (e.g., physicians' office visits, ED visits, infusion center visits, home health visits) during initial care and follow up	Unexpected visits, by site (e.g., physicians' office visits, ED visits, infusion center visits, home health visits)
	Expected visits, by site (e.g., physicians' office visits, ED visits, infusion center visits, home health visits)
	All visits (unexpected and expected), by site (e.g., physicians' office visits, ED visits, infusion center visits, home health visits)
Use of PICC line or central line to administer antibiotic therapy during initial care and follow up	PICC line or central line placement for antibiotic therapy
Infection-related healthcare visits (e.g., hospitalizations, ED visits, other outpatient visits) due to PICC line or central line used to administer antibiotic therapy during initial care and follow up	Unexpected visits due to PICC line (i.e. complications)
	Expected visits due to PICC line (i.e. initial placement, monitoring of PICC line)
	All visits due to PICC line (both unexpected and expected visits)
Response to treatment at end of therapy visit	Response to treatment (healthcare provider assessment) comparing response at the 10-14 day visit (end of therapy visit). Response to treatment will be defined

[figure not shown]

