2.1 Primary objective

Estimate the difference in infection-related total admitted hospital days during initial care (the date of enrollment to 10-14 days) and follow-up (30 days after initial care) comparing ABSSSI patients receiving care before implementation of the new critical pathway and after implementation.

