3.0 Study Design

This study will employ a “pre-post” pragmatic design, which will consist of both a pre-period, or an observational baseline period, and a post-period, or an interventional period. The pre-period and post-period will consist of independent groups of patients. During the pre-period, the site will implement the first component of the critical pathway through implementation of guideline-based criteria to identify patients admitted to the hospital, obtain informed consent, and monitor enrolled subjects. The site will initiate treatment for ABSSSI with “usual care,” defined as site- or physician-specific antibiotic treatment of ABSSSI with coverage for a known or suspected Gram-positive infection (e.g., vancomycin, linezolid, and daptomycin) to each study patient who meets all inclusion and exclusion criteria. Blinding of treating physician to patient enrollment in the study during the pre-period will ensure unbiased provision of usual care. During the post-period, for all patients who provide informed consent and are subsequently enrolled, each participating site will additionally implement the second component of the new critical pathway, use of dalbavancin, at the point of care in the hospital or other designated site to each study patient who meets all inclusion and exclusion criteria.

For both periods of interest, patient follow-up spans the period beginning on the day of study enrollment and ends 44 days thereafter, which incorporates an initial care period of 14 days (reflecting the 10–14-day period during which most antibiotics are anticipated to be required for care of ABSSSI) and a subsequent “follow-up” period of 30 days. Study measures will be collected as described in the protocol and will be based on medical records, unless otherwise indicated.

A schedule of assessments is provided in Appendix A. Follow-up visits will be scheduled for approximately 48-72 hours after enrollment (both periods), 10-14 days after enrollment (both periods), and 44 days after enrollment (both periods). Any additional visits to the visit schedule given in Appendix A will be at the discretion of the patient and treating physician.

The duration of the study was not predetermined; it is dependent on the time required to enroll the necessary number of eligible patients (43 patients per time period; 86 patients enrolled in all).

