4.2 Primary Outcome

The primary outcome (i.e., infection-related total number of days spent in hospital) will be assessed during the 44-day period of interest, including the initial-care period (i.e., beginning on the date of enrollment and ending 14 days thereafter) and the follow-up period (the 30-day period following initial care).

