4.3 Secondary Outcomes

Secondary outcomes will be assessed during initial care (the date of enrollment to day 14) and/or follow-up (30 days after initial care), and include:

[figure not shown]
[figure not shown]
Measure	Definition	Period of Assessment
Total admitted hospital days	Total length of stay (LOS) of all hospitalizations during the 44 days of the study (including initial hospitalization)	Initial care and follow-up
Infection-related major surgical interventions that required operating room time	Number of all, unexpected and expected infection-related major surgical interventions that required operating room time	Initial care and follow-up
Infection-related hospitalizations	Number of infection-related hospitalizations	Initial care and follow-up
Infection-related hospitalizations that resulted in admission to ICU	Number of infection-related hospitalizations resulting in admission to the ICU.	Initial care and follow-up
All-cause hospitalizations in the 30 days following discharge from the initial hospitalization	Number of all hospitalizations for patients after initial hospitalization discharge	Overall, including Initial care and follow-up
Infection-related ED visits	Number of all, unexpected and expected infection-related ED visits	Initial care and follow-up

[figure not shown]
Measure	Definition	Period of Assessment
Infection-related outpatient healthcare visits (e.g., physicians' office visits, ED visits, infusion center visits, home health visits)	Number of all, unexpected and expected infection-related outpatient healthcare visits, generated for all patients and repeated by site.	Initial care and follow-up
Use of PICC line or central line to administer antibiotic therapy	Number of PICC line or central line placement for antibiotic therapy	Initial care and follow-up
Infection-related healthcare visits (e.g., hospitalizations, ED visits, other outpatient visits) due to PICC line or central line used to administer antibiotic therapy	Number of all, unexpected and expected infection-related healthcare visits due to PICC line or central line used to administer antibiotic therapy	Initial care and follow-up
Response to treatment at end of therapy visit	Response to treatment will be defined through an assessment of erythema and the absence of fever at 10-14 days and will be categorized as a complete response, partial response, or failure.	Initial care

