6.2.4.2 Secondary Outcomes

Secondary Outcomes: Total Admitted Hospital Days

Total admitted hospital days will be calculated by two methods for the FAS population. First, LOS will be calculated by inpatient only stays and second, LOS will be calculated by inpatient stays including time spent in prolonged observation status (>1 day). The total admitted hospital-days will be assessed using a similar approach described for the primary analysis and will include all hospital stays. Tables will reflect descriptive statistics for total admitted hospital days and depicted graphically overall using box plots. Hypothesis testing will be performed by a two sided (two sample equal-variance) t-test, with a significance level of 0.05, comparing the difference in total time (in days) spent in hospital between the pre- and post-periods. Violations of assumptions for the t-test in the data will be checked for. An appropriate alternative method, such as the Mann-Whitney U test², will be selected if a major violation to an assumption of the t-test is present. Overall differences in descriptive statistics between the pre- and post-periods for total admitted hospital days will be reported.

Secondary Outcomes: Infection-Related Major Surgical Interventions that Required Operating Room Time

Infection-related major surgical interventions that required operating time will be displayed in tables by initial care, follow-up, and overall for the pre-period and post-period for the FAS population. Patient counts and percentages will be reported for no, any, expected, and unexpected surgical interventions. Differences in proportions between the pre- and post-period will be analyzed by a chi-square test or Fisher's exact test, as appropriate, and given with asymptotic 95% CIs.

Secondary Outcomes: Infection-Related Hospitalizations

Infection-related hospitalizations will be displayed in tables by initial care, follow-up, and overall for the pre-period and post-period for the FAS population. Patient counts and percentages will be reported for none, any, 1, 2, and ≥ 3 infection-related hospitalizations. Differences in proportions between the pre- and post-period will be analyzed by a chi-square test or Fisher's exact test, as appropriate, and given with asymptotic 95% CIs.

Secondary Outcomes: Infection-Related Hospitalizations that Resulted in Admission to ICU

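### Protocol Table 3 exchanges the descriptions of the primary outcome (infection-related hospital days) and the total-days secondary, and the SAP's only visible derivation is too ambiguous to settle which stays count

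*Protocol*

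**What the plan says.** **Protocol.** The primary objective (2.1) is to "Estimate the difference in infection-related total admitted hospital days during initial care" and follow-up. Table 3 in 4.1.2 then says what each outcome contains:

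- Primary, infection-related days: "Includes days during the initial hospitalization and all other hospitalizations".
- Secondary, total days: "Includes days during the initial hospitalization and all other infection-related hospitalizations".

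**SAP.** Section 4.2 states: "The primary outcome (i.e., infection-related total number of days spent in hospital) will be assessed during the 44-day period of interest". It gives a name and a window but no rule for which stays count. Section 4.3 defines the total-days secondary as "Total length of stay (LOS) of all hospitalizations during the 44 days of the study (including initial hospitalization", and section 6.2.4.2 says that this secondary "will be assessed using a similar approach described for the primary analysis and will include all hospital stays". Sections 2.1 and 6.2.4.1, and Table 7 in section 7.0, all label the primary as infection-related.

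The only visible derivation is the length-of-stay row of Appendix B. Its all-cause part sums end date minus start date plus one over hospitalizations. Its infection-related part is a single line that takes a subset of that all-cause time, for patients who had infection-related stays.

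SAP 5.0 covers laboratory-defined characteristics and the choice of tests. It does not mention Table 3.

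**The concern.** The two outcomes share the initial admission and the 44-day window. They can differ only in days spent in later hospitalizations unrelated to the infection. The rule that includes or excludes those days is therefore the whole difference between the primary and this secondary, and it is the part that Table 3 has the wrong way round.

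The primary t-test, the adjusted model and Table 7 all take this variable. If the rule can be read two ways, two competent programmers could produce different primary results from the same documents. The comparison is also unrandomised and sequential, so an unsettled definition leaves room to choose between an infection-related and an all-cause result after the data are seen.

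**Working it through.** **1. The plan's own figure.** Inputs from Protocol 6.3: difference 2 days, SD 3.0, two-sided alpha 0.05, power 80%.

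- Normal approximation: n = 2(1.960 + 0.842)² × 3.0² / 2² = 2 × 7.849 × 2.25 = 35.3, so 36 per period.
- The t-test calculation gives 36.3, so 37 per period, as stated, with power 0.808 at 37.

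The sample size reproduces and is not in dispute here.

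**2. The definitions side by side.**

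| Place | Primary (infection-related days) | Secondary (total days) |
|---|---|---|
| Protocol 2.1 | Infection-related | – |
| Protocol Table 3 | Initial stay plus every other hospitalization | Initial stay plus infection-related hospitalizations |
| SAP 4.2 | Infection-related, no rule for stays | – |
| SAP 4.3 and 6.2.4.2 | – | Every hospitalization |
| SAP Appendix B, literal | All-cause days of patients with an infection-related stay | All-cause days |

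A total cannot be smaller than one of its parts. Under Table 3 the total could never exceed the infection-related count, and it would fall below that count whenever an unrelated readmission occurred. That is enough to show that the descriptions are exchanged. The synopsis lists the two outcomes in the opposite order from Table 3, which would fit labels having been reordered without their descriptions. That explanation is inference.

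**3. Appendix B read literally.** The restriction selects patients. Subjects are recruited among patients admitted for treatment of ABSSSI (synopsis, Population; Protocol 3.4.1), so each should have at least one infection-related stay. The selection keeps essentially everyone and, for each of them, all of the all-cause time. The primary then equals the all-cause secondary.

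**4. One patient (assumed figures).** Initial ABSSSI stay of 4 days, later unrelated stay of 5 days, both inside the window.

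- Only infection-related stays counted: primary = 4, total = 4 + 5 = 9.
- Table 3 as printed: primary = 9, total = 4.
- Appendix B read literally: primary = 9, total = 9.

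The primary has two candidate values, 4 or 9.

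**5. Scale.** With 43 patients per period (Protocol 6.3), one such 5-day stay moves its period's mean by 5/43 = 0.116 days. That is 0.116/2 = 5.8% of the planned 2-day difference. If unrelated days are balanced between periods, the expected contrast does not move. With no unrelated readmissions, every reading gives the same number. The documents give no readmission rate, so no actual size can be computed.

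**The case against.** The strongest reply is that the SAP governs the analysis and is consistent about the name of the primary. It also defines the total-days secondary correctly and plans separate box plots for all-cause and infection-related time. Reading Appendix B by patient would make the primary and a named secondary identical and one of those figures redundant, so a stay-level rule was probably meant. The cross-reference in SAP 3.0, "Study measures will be collected as described in the protocol and will be based on medical records, unless otherwise indicated", concerns data collection and does not send a programmer to Table 3 for a derivation. The table shells are a separate document that is not available here, and they or redacted text may hold the rule.

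Most of this stands, and it limits the point. It does not remove it. The protocol's outcome table still states the opposite of the objective, the section meant to list departures does not mention it, and the one visible derivation needs inference to be read as intended.

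Three stronger readings are tempting, and the documents do not support them:

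- **The primary will be analysed as all-cause.** The consistent labels in the SAP point the other way. What is shown is a wrong protocol description and an ambiguous derivation.
- **The study loses power.** The direction depends on whether the 3.0-day SD describes infection-related or total days, and no passage says. If it describes infection-related days, adding independent unrelated days would raise the variance. If it already describes total time, an all-cause primary loses nothing against plan.
- **The sample size text should be relabelled as infection-related.** Protocol 6.3 and SAP 6.1.2 speak of total hospital time. Relabelling would assert, without support, that the 4.0-day mean and 3.0-day SD describe infection-related days.

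**Conclusion.** The point holds as an error in the definition of the primary outcome. Table 3 is wrong as written, SAP 5.0 does not correct it, and Appendix B is ambiguous where it should settle the matter. The intended variable, days in infection-related stays only, can be inferred from the objective, the labels in the SAP and the definition of the secondary, but no visible passage states it as a rule.

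The conclusion about Table 3 rests on the text alone. The conclusion about Appendix B assumes a literal reading and that every enrolled subject's initial admission counts as infection-related. The per-readmission shift assumes a 5-day stay and 43 patients analysed per period, and it is an illustration, not an estimate. The case for correction is that the primary variable should be fixed in writing before database lock, whatever the eventual size.

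**What to change.** 1. Exchange the two descriptions in Protocol Table 3. If the protocol is not to be amended, record the correction in SAP 5.0.
2. Replace the infection-related line in SAP Appendix B with: *Sum LOS only over hospital stays recorded as infection-related.* Leave the date rules unchanged. Refer to the same stay-level classification that is already needed for the secondary outcome defined in SAP 4.3 as "Number of infection-related hospitalizations".
3. Optionally, name the infection-related variable in the test sentence of SAP 6.2.4.1, which now speaks only of total time in hospital.
4. Leave the sample size text in Protocol 6.3 and SAP 6.1.2 as it is.

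The cost is two table cells and one derivation line. A protocol change needs IRB approval and a signed page under Protocol 9.1, and a note in the SAP is the lighter route. No new data are needed.
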